9.1.5. Follow-Up Phase

The posttreatment Follow-up Phase will begin once the subject completes the End-of-Treatment evaluation. Reasons for discontinuation of study treatment are listed in Section 10.2. Subjects who discontinue treatment before disease progression must continue to have disease evaluations as described in Table 1 and Section 9.4 (every 6 weeks [± 1 week] for the first 12 months of after the start of treatment and every 9 weeks [± 1 week] thereafter regardless of treatment delays). After disease progression is confirmed, follow-up for survival status and subsequent anti-cancer therapy will be obtained at least every 12 weeks after the last dose of study drug, until the subject has died, is lost to follow-up, or has withdrawn consent. If the information on survival status is obtained via telephone contact, written documentation of the communication must be available for review in the source documents. If the subject has died, the date and cause of death will be collected and documented on the CRF.

The end of the study is anticipated to be 24 months after the last subject has been enrolled (last patient in) or when the last subject has the last assessment in this study (eg, last survival follow-up for the last subject), whichever occurs first.

Investigators may recontact the subject to obtain long-term follow-up information regarding the subject's safety or survival status as noted in the informed consent form (refer to Section 16.2.3, Informed Consent).

Subjects will be instructed that study drug will not be made available to them after they have completed/discontinued study drug and that they should return to their primary physician to determine standard of care.

Beginning with the implementation of Amendment 7, data from safety evaluations performed according to local regulatory approvals and standard of care guidelines^{50,51} will no longer be collected with the exception of serious adverse events that are to be reported and entered in the Sponsor safety repository.

9.2. Procedures for Subjects Continuing on Study with Atezolizumab Monotherapy (per Amendment 6)

Subjects who had received combination therapy will have the opportunity to receive atezolizumab monotherapy, per the schedule in Table 1 and Section 6.2, and will complete adverse event follow up as defined in Section 12.4.

Subjects remaining in the study on atezolizumab monotherapy will no longer require pharmacokinetic, immunogenicity, or biomarker assessments. Therefore, only the Table 1 assessments will be performed for these subjects (assessments in Table 2 through Table 7 included in previous versions of this protocol will no longer be followed and were removed). Treatment-related information, such as exposure data, adverse events, and disease assessments, will continue to be collected and treatment with atezolizumab will continue until the criteria in Section 10.2 is met. As no new subjects will be initiating therapy, treatment beyond initial radiographic progression will no longer be allowed without prior consultation with the Sponsor's Study Responsible Physician.

Safety Assessments

Safety reporting for those continuing on atezolizumab monotherapy is described in Section 12.4. Laboratory and other safety assessments will continue as in Table 1 and in Section 9.7.

Disease Evaluations

Disease evaluations, including assessment of response, will be conducted by the site, as described in Table 1 and Section 9.4.

9.3. Guidance for Subjects Continuing on Study with Atezolizumab Monotherapy (per Amendment 7)

The third planned DMC review (23 May 2018) determined that the addition of daratumumab to atezolizumab did not result in additional clinical benefit. As a result, further treatment with daratumumab was discontinued (with implementation of Amendment 6) and data collection will cease after locking of the clinical database (with implementation of Amendment 7). For those subjects who are deriving clinical benefit from atezolizumab monotherapy, but do not have access to commercial atezolizumab, treatment may continue under the supervision of treating investigators in accordance with local regulatory approvals and standard of care guidelines.^{50,51} Prior to the administration of atezolizumab, investigators will be required to submit documentation of subject response and clinical status to the Sponsor, either electronically or via facsimile.

Data from these safety and efficacy evaluations will no longer be collected with the exception of serious adverse events that are to be reported and entered in the Sponsor safety repository. Study drug accountability must continue to be monitored and documented by the study site.

9.4. Efficacy Evaluations

Beginning with the implementation of Amendment 7, efficacy evaluations will be performed by the investigator according to local regulatory approvals and standard of care guidelines.^{50,51} These data will no longer be collected by the Sponsor.

Efficacy evaluations will be performed as shown in the Time and Events Schedule (Table 1), per RECIST 1.1 (Attachment 5) and irRECIST (Attachment 6). Results will be evaluated by the investigator and recorded in the CRF. Subjects will undergo tumor assessments until radiographic disease progression, or withdrawal of consent, study termination by Sponsor, or death, whichever occurs first. For subjects who discontinue treatment for reasons other than progression (eg, adverse event), disease assessments may be discontinued. Subjects who have documented disease progression should discontinue study therapy.

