Tumor assessment CT or MRI imaging of all disease sites documented at Screening should be performed using the same methodology throughout the study. Tumor assessments will be performed per RECIST 1.1. For subjects who discontinue treatment for reasons other than progression (eg, adverse event), tumor assessments will continue to be performed until documented disease progression or a new cancer therapy is initiated.			CT or MRI of head, chest, abdomen, and pelvis are required. Include neck if clinically indicated and any other known site of active disease.		X CT or MRI of chest and abdomen (and known sites of active disease) Every 6 weeks (±1 week) for the first 12 months of treatment and every 9 weeks (±1 week) thereafter regardless of treatment delays. Same frequency for all subjects. Imaging timepoints should be calculated from the date of C1D1.							

Table 1: Time and Events Schedule – Safety Run-in, Randomized Arms

Beginning with the implementation of Amendment 7, subjects who continue to derive benefit from atezolizumab treatment, may continue to receive atezolizumab under the supervision of treating investigators in accordance with local regulatory approvals and standard of care guidelines.^{50,51} Data from efficacy and safety evaluations performed according to local regulatory approvals and standard of care guidelines^{50,51} will no longer be collected with the exception of serious adverse events that are to be reported and entered in the Sponsor safety repository.

Assessments	Prescreening (optional)	Screening		Treatment Period (21-day cycles)						EOT (30 +7d after last dose)	Follow-up Period	
				Arm	Cycles 1-3				Cycle 4 and beyond		Pre-PD	Post-PD Survival
					D1 (±3)	D2	D8 (±1)	D15 (±1)				
Day	Any time prior to start of Screening	-56 to -1	-28 to -1									
Laboratory Assessments:												

 - Refer to Inclusion Criterion 6 for specific laboratory values that must be met prior to first dose of study drug administration. - C1D1 laboratory assessments (hematology, chemistry) may be omitted if Screening tests were performed ≤ 7 days prior to the first administration of study drug and the results meet eligibility criteria. After Cycle 1, predose laboratory tests can be conducted up to 72 hours prior to dosing. Laboratory test results must be reviewed by the investigator or qualified designee and found to be acceptable prior to administration of each dose of study drug. 												

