For Arm B, daratumumab will be administered intravenously (IV) at 16 mg/kg weekly on Days 1, 8, and 15, for the first 3 cycles, then on Day 1 of each 21-day cycle thereafter. Atezolizumab will be administered at 1,200 mg IV on Day 2 of Cycle 1 only and then on Day 1 of every 21-day cycle thereafter. Measures to prevent infusion-related reactions will include preinfusion medication (see Section 6.3). Subjects will be monitored closely for immune-mediated adverse events including pneumonitis, enterocolitis, hepatitis, dermatitis, neuropathies, and endocrinopathies.

Study visits for subjects receiving daratumumab (Safety Run-in and Arm B) will occur weekly during the first 3 cycles and every 3 weeks for all cycles thereafter. Study visits for subjects randomized to Arm A (atezolizumab alone) will occur weekly during the first 2 cycles and every 3 weeks thereafter. Subjects will continue on the assigned study treatment (atezolizumab alone or atezolizumab + daratumumab) until treatment discontinuation due to disease progression, unacceptable toxicity, or other protocol-defined treatment discontinuation criteria (see Section 10.2); or until subjects in Arm A crossover. Subjects in Arm B, who experience unacceptable toxicity directly attributable to one agent and who are experiencing clinical benefit (ie, stable disease or better) may stay on the other agent until treatment discontinuation criteria

[figure not shown]
are met, after discussion with the Sponsor. Subjects who have crossed over and experience unacceptable toxicity directly attributable to atezolizumab and who are experiencing clinical benefit (ie, stable disease or better) may stay on daratumumab until treatment discontinuation criteria are met, after discussion with the Sponsor.

Follow-up

The Follow-up phase will begin after the End-of-Treatment visit, 30 (+7) days after the discontinuation of the study drugs. Subjects will be followed for survival every 12 weeks after confirmed disease progression or start of new anticancer therapy. For subjects who discontinue treatment for reasons other than progression (eg, adverse event), disease assessments will continue to be performed until disease progression or a new cancer therapy is initiated (or another study withdrawal criterion is met, see Section 10.2).

The timing of assessments is provided in the Time and Events Schedule (Table 1). A diagram of the study design is provided in Figure 1.

Figure 1: Schematic Overview of the Study

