5.3.3. Progression Free Survival

Definition

Progression-free survival (PFS) is measured from randomization until the first documented disease progression or death, whichever occurs first. PFS will be censored on the date of last tumor assessment documenting absence of tumor progression for subjects who have no documented progression and are still alive prior to data cutoff, dropout, lost to follow-up or the initiation of Subsequent anti-cancer treatment. Subjects with no tumor assessments after randomization their PFS will be censored on the date of randomization. PFS is calculated in months as follows:

$$\text{PFS} = (\text{date of PD/death or censoring} - \text{date of randomization} + 1) / (365.25/12).$$

Analysis Methods

The number and percentage of subjects who had a PFS event or were censored will be reported. The Kaplan-Meier method will be used to estimate the distribution of overall PFS for each treatment group, and the median PFS with 95% CI will be provided. In addition, the Kaplan-Meier PFS curve will also be presented by treatment group.

Hazard ratio (Arm B vs. Arm A) and its 95% confidence interval will be presented. In addition, 3, 6, 12-months of PFS rate with 95% CI will be estimated by Kaplan-Meier method and reported for each treatment group.

PFS will also be presented by the subgroups specified in Section 2.4, as appropriate.

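### Protocol 9.4 lets disease assessments stop when treatment ends without progression, against four other places in the protocol; PFS and duration-of-response censoring could become informative wherever 9.4 was followed

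*Protocol*

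**What the plan says.** Protocol 9.4 (Efficacy Evaluations) contains this sentence: "For subjects who discontinue treatment for reasons other than progression (eg, adverse event), disease assessments may be discontinued". The sentence before it reads: "Subjects will undergo tumor assessments until radiographic disease progression, or withdrawal of consent, study termination by Sponsor, or death, whichever occurs first". Stopping treatment is not among those end points.

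Four other places in the current text give the opposite rule for the same subjects:

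- The Synopsis (Efficacy Evaluations) and Section 3.1 (Follow-up) both say that "disease assessments will continue to be performed until disease progression or a new cancer therapy is initiated", or until another withdrawal criterion applies.
- Table 1, tumor assessment row: "tumor assessments will continue to be performed until documented disease progression or a new cancer therapy is initiated".
- Section 9.1.5: "Subjects who discontinue treatment before disease progression must continue to have disease evaluations as described in Table 1 and Section 9.4".

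Section 10.2 supports these in general terms: follow-up assessments continue on the Time and Events Schedule after treatment stops.

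On the analysis side, SAP 5.3.3 states that "PFS will be censored on the date of last tumor assessment documenting absence of tumor progression" when there is no documented progression and the subject is alive. SAP 5.3.1 also uses the last disease assessment as the censoring date for duration of response. SAP 5.1.2 plans no imputation of missing efficacy values. The SAP has no PFS or duration-of-response sensitivity analysis for subjects whose scans stopped.

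**The concern.** A site can comply with 9.4 and breach 9.1.5, or the reverse. If it follows 9.4, a subject who stops for toxicity has no later scan. PFS is then censored at about the time of stopping, or counted only at a later death. A responder in the same position has no observable end of response.

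Stopping for toxicity is unlikely to be unrelated to prognosis, so this censoring may be informative. The trial is open-label and one arm receives an added drug with its own stopping rules, so the amount of such censoring could differ by arm. Section 3.4 defends the open-label design by equal assessment frequency, adherence to the schedule and predefined censoring rules. An optional stop to scanning weakens that defence.

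**Working it through.** **Step 1: do the cross-references settle the conflict?** They do not. Section 9.4 refers to Table 1 for the schedule, and Table 1 requires continued scans. Section 9.1.5 sends the reader to both Table 1 and 9.4, and so does 9.2. The Amendment 7 paragraph at the head of 9.4 is tied to that amendment; the disputed sentence carries no date. Under Amendment 6, Section 3.2 keeps Table 1 procedures in force until database lock, and 9.2 keeps disease assessments among the data collected.

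**Step 2: what could it do to the PFS hazard ratio?** The documents give no event count, power or stopping rate by arm for PFS, so there is no figure to reproduce. The following is an illustration.

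Inputs from the protocol:

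- Six-month PFS of 29% (Table 4, second-line, TC2/3 or IC2/3). Hazard = −ln(0.29)/6 = 0.206 per month; median = ln 2/0.206 = 3.4 months.
- 8% stopping for adverse events on atezolizumab (Section 1.2, the Phase 3 comparison with docetaxel).
- Six-month OS of 76% (Table 4, same column).

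Assumptions not in the documents:

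- No treatment effect while on treatment.
- A fraction f stops before progression, with stopping hazard 0.206 × f/(1 − f); f = 8% in Arm A and 8%, 15% or 25% in Arm B.
- Progression hazard after stopping multiplied by 1, 2 or 3, the same in both arms.
- Data cutoff at 12 months.
- For the last column, death after the unobserved progression at 2 × (−ln(0.76)/6) = 0.091 per month.

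Cox hazard ratios (B vs A) from 400,000 simulated subjects per arm:

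| Stop A / B | Hazard after stop | Scans continue | Scans stop, censored | Scans stop, later death counted |
|---|---|---|---|---|
| 8% / 8% | ×2 | 1.00 | 1.00 | 1.00 |
| 8% / 15% | ×1 | 1.00 | 1.00 | 0.92 |
| 8% / 15% | ×2 | 1.04 | 1.00 | 0.94 |
| 8% / 15% | ×3 | 1.05 | 1.00 | 0.94 |
| 8% / 25% | ×1 | 1.00 | 1.00 | 0.82 |
| 8% / 25% | ×2 | 1.10 | 1.00 | 0.85 |
| 8% / 25% | ×3 | 1.14 | 1.01 | 0.86 |

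**Step 3: reading the table.** In this setting bias needs different stopping rates by arm. Under plain censoring it also needs a changed progression risk after stopping. SAP 5.3.3 counts death as a PFS event, so some subjects would fall in the last column. Counting those deaths does not shrink the distortion here: a death dated well after a missed progression is a late event, and it lengthens apparent PFS in the arm with more stopping.

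**Step 4: size against noise.** With 44 per arm, even if all 88 subjects had an event, the standard error of the log hazard ratio is about √(4/88) = 0.21. From the unrounded ×2 results, the shift under censoring is ln(1.036) − ln(1.002) = 0.03 at 15% stopping and ln(1.097) − ln(0.996) = 0.10 at 25%. That is at most about half a standard error.

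**The case against.** The strongest reply is about dating. The Amendment 2 log records that a sentence was added at the end of this paragraph, on continuing evaluations in subjects treated past progression. The paragraph now ends with an instruction to stop therapy on documented progression, which matches the Amendment 6 log. After Amendment 2, only the logs for Amendments 6 and 7 list the Efficacy Evaluations section as changed. Sections 3.2 and 17.9.1 base the clinical study report on the data reviewed on 23 May 2018. If the disputed sentence came with Amendment 6, its effect on that report is nil. From then on nobody receives daratumumab, so the difference between arms that drives the illustration largely disappears. This is plausible but remains inference, because no log quotes the sentence.

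The second reply is about the inputs, and it stands. Nothing in the documents supports 15% to 25% stopping in Arm B. Section 3.1 lets a benefiting Arm B subject with toxicity from one agent stay on the other, which limits full discontinuation. Section 1.4 expects no overlapping toxicities and reports that the DMC saw no unexpected toxicity imbalance.

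Third, PFS and duration of response are secondary and are reported with estimates and intervals; the current text plans no test. The effect on duration of response is not quantified here.

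A reader might go further and infer that 9.4 concealed a worse PFS in the combination arm, given the larger number of deaths noted in Section 1.4. The documents do not support that. They show neither that any site stopped scans under 9.4, nor that stopping differed by arm, nor that the sentence was in force before the data cut.

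**Conclusion.** The contradiction is real and in the current text: one permissive sentence in 9.4 against the Synopsis, Table 1, 3.1 and 9.1.5, and against its own preceding sentence. With the SAP's last-assessment rule and no imputation, following 9.4 could make PFS and duration-of-response censoring informative.

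The size is unknown. On assumed inputs (8% against 15% to 25% stopping, hazard doubled afterwards) a hazard ratio of about 1.04 to 1.10 becomes about 1.00. It would be wrong to read these figures as upper bounds on the ground that later deaths are still counted: with the death hazard assumed here, counting them gives 0.94 to 0.85, further from the value with continued scans.

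If the sentence postdates 23 May 2018, the study report is untouched and the point concerns only data collected between then and database lock. If it is earlier, the concern applies to the reported PFS and duration of response. Severity is low to moderate: worth correcting, not critical.

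**What to change.** Reconcile 9.4 with the Synopsis, Table 1, 3.1 and 9.1.5, so that one rule on assessments after a stop without progression covers all data up to database lock. State which amendment introduced the 9.4 sentence and which dates and subjects it covers. Adopting the rule already in the other four places would change one sentence and add no scans beyond those already required.

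Rewording cannot recover missed scans: the Amendment 7 rationale says the database is locked, and efficacy data are no longer collected. So also report by arm, from existing data, how many subjects were censored for PFS and for duration of response after stopping treatment without progression, with the reason for stopping. This costs one table. If the counts differ by arm, add a PFS sensitivity analysis that counts discontinuation for toxicity as an event.

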9.4.1. Disease Assessments

Screening Tumor Assessments

Screening tumor assessments will include CT scans (with IV contrast unless contraindicated) or MRIs of the chest, abdomen, head, and pelvis. For subjects with known bone lesions, CT, or MRI scan of the affected area of bone will be required at Screening. Additionally, CT scans of the neck should also be performed at Screening if clinically indicated. Subjects who are intolerant to IV contrast agents or in whom IV contrast is contraindicated may have CT scans performed with oral contrast; the reason for not using IV contrast must be noted in the source documents. At the investigator's discretion, other methods of assessment of measurable disease (eg, physical examination) as per RECIST 1.1 may be used.

Magnetic resonance imaging may be used to evaluate sites of disease that cannot be adequately imaged using CT or if IV and oral contrast for CT scan are contraindicated. In any case where an MRI is performed, it must be the imaging technique used to assess disease at Screening and at all subsequent response evaluations.

Tumor assessments performed as standard of care prior to obtaining informed consent and within 28 days of Cycle 1, Day 1 may be used rather than repeating tests. All known sites of active disease must be documented at Screening.

Subsequent Tumor Assessments

At each subsequent tumor evaluation, chest and abdomen CT scans or MRIs, in addition to any other known sites of active disease, will be performed. The same radiographic procedure used to assess disease sites at Screening should be used throughout the study (eg, the same contrast protocol for CT scans). Response will be assessed by the investigator using RECIST 1.1; irRECIST will also be used for exploratory purposes.

Deterioration of health status requiring discontinuation of study treatment without objective evidence of progressive disease should be reported as "clinical disease progression". Every effort should be made to document objective progression via radiographic confirmation.

Subjects in Arm A who crossed over to Arm B after confirmed disease progression should be carefully evaluated to determine whether they will benefit from treatment with atezolizumab monotherapy.

9.4.2. Treatment After Initial Disease Progression

Anti-tumor response patterns seen with immunotherapeutic agents may extend beyond the typical time course of responses seen with cytotoxic agents. Therefore, the investigator may decide to continue a treatment with study drug beyond tumor progression determined on the basis of the RECIST 1.1 criteria. Any treatment beyond disease progression requires prior discussion with and approval by the Sponsor's Study Responsible Physician.

Once the specific criteria of RECIST 1.1 defined disease progression are met, a repeat efficacy evaluation should be performed at the next per protocol scheduled assessment timepoint or earlier, if clinically necessary, but no sooner than 4 weeks from the previous assessment, in order to confirm disease progression. This allowance to continue treatment despite initial radiologic progression takes into account the observation that some subjects can have a transient tumor flare in the first few months after the start of immunotherapy but develop subsequent disease response. Subjects should continue study treatment at the discretion of the treating physician while waiting for confirmation of disease progression if they are clinically stable as defined by the following criteria:

- Absence of clinical signs and symptoms indicating disease progression
- Clinical disease progression not requiring immediate therapeutic intervention
- No decline in ECOG performance status
- Absence of progressive tumor at critical anatomical sites (eg, cord compression) requiring urgent alternative medical intervention

Subjects that are deemed clinically unstable are not required to have imaging assessments and can be taken off study treatment.

[Table 12](#) provides guidelines to continue or discontinue study drug based on the initial and subsequent assessments of the tumor and the clinical status.

Table 12: Imaging and Treatment after First Radiologic Evidence of Progressive Disease

	Clinically Stable	Clinically Unstable
	Additional Imaging and Treatment	Additional Imaging and Treatment
1st radiologic evidence of PD by RECIST 1.1	Any treatment beyond first disease progression requires prior discussion with and approval by the Sponsor's Study Responsible Physician. If continued treatment is approved by Sponsor's Study Responsible Physician, imaging should be repeated ≥ 4 weeks later (or the next protocol specified timepoint) to confirm PD.	Repeat imaging at ≥ 4 weeks to confirm PD per investigator's discretion only and subject should discontinue study treatment
Repeat tumor imaging confirms PD by RECIST 1.1	No additional imaging required if the subject discontinues study treatment.	No additional imaging required and subject should discontinue study treatment
	Regularly scheduled imaging should be performed if the subject continues on study treatment (exception to continue study treatment is possible upon consultation with Sponsor).	
Repeat tumor imaging does not show PD by RECIST 1.1	Regularly scheduled imaging should be performed while the subject continues on study treatment.	Continue regularly scheduled imaging assessments, per investigator's discretion. Subject may restart study treatment if condition has improved or clinically stable per investigator's discretion, upon consultation with Sponsor.

